### **DOCUMENT HISTORY**

Document	Date of Issue	Overall Rationale
Amendment 5	02-DEC-2022	The key reasons for this amendment are to: 1) allow for over enrollment of participants in the study and 2) allow for local sourcing of placebo.
Amendment 4	01-APR-2022	The primary purpose of this amendment is to: 1) Clarify that blood collection for participants with an anaphylaxis or hypersensitivity AESI of Grade 3 or 4 is to assay for potential ADA to MK-1654, and additional ADA characterization, if indicated; 2) Add China-specific protocol requirements for a separate, additional swab collection for COVID-19 testing.
Amendment 3	29-SEP-2021	The primary purpose of this amendment is to: 1) Provide additional guidance on respiratory infection assessment and nasopharyngeal (NP) sample collection; and 2) Add Chinaspecific protocol requirements.
Amendment 2	23-APR-2021	The purpose of this amendment is to address regional Health Authority feedback.
Amendment 1	08-FEB-2021	The primary purpose of this amendment is to add changes that align with the pediatric development plan and changes in severity grading of adverse events, which has been adapted from the National Cancer Institute Common Terminology Criteria for Adverse Events (NCI CTCAE) version 5.0.
Original Protocol	28-JUL-2020	Not applicable.

C Confidential

PROTOCOL/AMENDMENT NO.: 004-05

### PROTOCOL AMENDMENT SUMMARY OF CHANGES

**Amendment:** 05

### **Overall Rationale for the Amendments:**

The key reasons for this amendment are to: 1) allow for over enrollment of participants in the study and 2) allow for local sourcing of placebo.

## **Summary of Changes Table:**

Section # and Name	Description of Change	Brief Rationale
Section 1.1 Synopsis Section 1.2 Schema Section 4.1 Overall Design Section 6.3.2 Stratification Section 8.13.4 Early Withdrawal Visit Section 9.1 Statistical Analysis Plan Summary Section 9.7 Interim Analyses Section 9.9.1.1 Sample Size and Power for Testing the Primary Efficacy Hypothesis	
 
Updated content to allow for over enrollment up to 10%. Made updates for these additional participants to be enrolled and followed through Day 365 (RSV Season 1 only).
 
Adjusted the early and moderate pre-term infant enrollment from at least 20% of participants to at least 600 participants.
 
	
 
To ensure that a sufficient number of participants are enrolled to support registration. Additional participants do not need to be followed through Day 515.
 
Adjusted early and moderate preterm infant enrollment to align with absolute count originally anticipated to be enrolled.
 

Section # and Name	Description of Change	Brief Rationale	
Section 4.1 Overall Design Section 6.1 Study Intervention(s) Administered Section 6.2.1 Dose Preparation	
 
Removed "USP" from placebo description.
 
Changed dose formulation from vial to sterile solution.
 
Added local sourcing option for placebo.
 
	Allow for local sourcing of placebo.	
Title Page Section 10.1.1 Code of Conduct for Clinical Trials Throughout	Sponsor entity name and address change.	Merck Sharp & Dohme Corp. underwent an entity name and address change to Merck Sharp & Dohme LLC, Rahway, NJ, USA. This conversion resulted only in an entity name change and update to the address.	
Title Page	Added EU CT study identifier.	EU CT number now available.	
Section 1.1 Synopsis Section 6.1 Study Intervention(s) Administered	
 
Descriptions of Use and NIMP have been updated:
 
NIMP to NIMP/AxMP
 
For use, experimental to test product; placebo to comparator
 
The note in Table 2 describing the classification IMP and NIMP/AxMP was edited accordingly.
 
	Per Regulation (EU) No 536/2014 of the European Parliament and of the Council	

6

PROTOCOL/AMENDMENT NO.: 004-05

Section # and Name	Description of Change	Brief Rationale		
Section 1.3.2 Schedule of Activities – RSV Season 2 (First 1650 Participants)	Removed "Start of RSV Season 2 follow-up" and "End of RSV Season 2 follow-up" from Visits 7 and 8, respectively, and the notes.	The beginning and end of the RSV Season 2 may not align with study Days 365 and 515, respectively, due to the changing epidemiology of RSV disease due to the COVID-19 pandemic.		
Section 4.4 Beginning and End of Study Definition	Added text defining the local start of the study for countries in the European Economic Area as First Site Ready in any Member State.	Per Regulation (EU) No 536/2014 of the European Parliament and of the Council		
Section 5 Study Population	Added text regarding the Code of Conduct for Clinical Trials at the beginning of this section.	To clarify the collection, use, and confidentiality of demographic data provided by the participants.		
Section 8.4 Adverse Events, Serious Adverse Events, and Other Reportable Safety Events Section 10.3.1 Definitions of	Added definitions for medication error, misuse, or abuse and the need for investigator to report instances as an AE or SAE.	Per Regulation (EU) No 536/2014 of the European Parliament and of the Council		
Medication Error, Misuse, and Abuse				
Section 8.13.3 Delay in Randomization and Study Medication Administration	Text was updated to associate Day 1 with the day study medication is administered, not the day screening procedures are performed.	Clarification to define Day 1 if screening and dosing do not occur the same day.		

PROTOCOL/AMENDMENT NO.: 004-05

Section # and Name	Description of Change	Brief Rationale		
Section 9.4.1 Efficacy/ Pharmacokinetics/ Pharmacodynamics/ Immunogenicity Endpoints	Tertiary efficacy endpoints were added to evaluate RSV-associated outpatient and inpatient ARI.	To evaluate efficacy endpoints of interest for the study.		
Section 10.1.7 Compliance with Law, Audit, and Debarment	Added content to immediately report any serious/suspected serious breaches.	Per Regulation (EU) No 536/2014 of the European Parliament and of the Council		
Section 8.1.1.1 General Informed Consent Section 10.7.3 China	Added specifications for informed consent for participants in China.	Align with local regulatory guidelines.		
Section 10.7.3 China	Updated timing of COVID-19 swab collection.	Clarification and to align with standard of practice.		
Throughout document	Minor administrative, formatting, grammatical, and/or typographical changes were made throughout the document.	To ensure clarity and accurate interpretation of the intent of the protocol.		

7

### 1 PROTOCOL SUMMARY

### 1.1 Synopsis

**Protocol Title:** A Phase 2b/3 Double-Blind, Randomized, Placebo-Controlled Study to Evaluate the Efficacy and Safety of MK-1654 in Healthy Pre-Term and Full-Term Infants

**Short Title:** Efficacy and Safety of MK-1654 in Healthy Pre-term and Full-Term Infants

Acronym: Not applicable

### Hypotheses, Objectives, and Endpoints:

Hypotheses are aligned with objectives in the Objectives and Endpoints table.

The following objectives will be evaluated in healthy pre-term and full-term infants receiving a single IM dose of MK-1654 or placebo.

Primary Objectives	Primary Endpoints
- To evaluate the efficacy of MK-1654 compared to placebo as assessed by the incidence of RSV-associated MALRI (outpatient and inpatient) from Days 1 through 150 postdose.  Hypothesis: Administration of MK-1654 reduces the incidence of RSV-associated MALRI from Days 1 through 150 postdose compared to placebo (The statistical criterion for success requires the lower limit of the 95% CI for efficacy to be greater than 25%).	
 
RSV-associated MALRI (outpatient and inpatient), defined as the following seen in an outpatient or inpatient clinical setting:
 
Cough or difficulty breathing; AND
 
1 or more of the following: wheezing, chest wall in-drawing/retractions, rales/crackles, hypoxemia, tachypnea, dehydration due to respiratory symptoms; AND
 
RSV-positive RT-PCR NP sample
 

- To evaluate the safety and tolerability of
MK-1654 compared to placebo as assessed
by the proportion of participants
experiencing AEs.

- Solicited injection-site AEs from Days 1 through 5 postdose
- Solicited daily body temperature, with fever defined as rectal temperature ≥102.2°F (≥39.0°C) or axillary temperature ≥101.7°F (≥38.7°C), from Days 1 through 5 postdose
- Solicited systemic AEs from Days 1 through 5 postdose
- Anaphylaxis/hypersensitivity AESI from Days 1 through 42 postdose
- Rash AESI from Days 1 through 42 postdose
- Nonserious AEs from Days 1 through 42 postdose
- SAEs through the duration of study participation

### Secondary Objectives

## Secondary Endpoints

**AND** 

Confidential

- To evaluate the efficacy of MK-1654 compared to placebo as assessed by the incidence of RSV-associated hospitalization from Days 1 through 150 postdose.
- Hypothesis: Administration of MK-1654 reduces the incidence of RSV-associated hospitalization from Days 1 through 150 postdose compared to placebo (The statistical criterion for success requires the lower limit of the 95% CI for efficacy to be greater than 0%).
- RSV-associated hospitalization, defined as the following:Hospital admission for respiratory illness;
- RSV-positive RT-PCR NP sample

- To estimate the efficacy of MK-1654 compared to placebo as assessed by the incidence of RSV-associated MALRI (outpatient and inpatient) from Days 1 through 180 postdose.
- RSV-associated MALRI (outpatient and inpatient), defined as above

PROTOCOL/AMENDMENT NO.: 004-05

### **Overall Design:**

Study Phase	Phase 2/Phase 3							
Primary Purpose	Prevention							
Indication	Respiratory syncytial virus infection							
Population	Healthy pre-term and full-term infants							
Study Type	Interventional							
Intervention Model	Parallel This is a multi-site study.							
Type of Control	Placebo							
Study Blinding	Double-blind with in-house blinding							
Blinding Roles	Participants or Subjects Investigator Sponsor							
Estimated Duration of Study	The Sponsor estimates that the study will require approximately 3.5 years from the time the first participant's legally acceptable representative provides documented informed consent until the last participant's last study-related contact. For purposes of analysis and reporting, the overall study ends when the Sponsor receives the last laboratory result or at the time of final contact with the last participant, whichever comes last.							

# **Number of Participants:**

Approximately 3300 participants will be allocated/randomized in this study as described in Section 9.9.

## **Study Governance Committees:**

Steering Committee	No								
Executive Oversight Committee	Yes								
Data Monitoring Committee	Yes								
Clinical Adjudication Committee	No								
Study governance and SAC considerations are outlined in Appendix 1 (Section 10.1.4).									

## **Study Accepts Healthy Volunteers:** Yes

A list of abbreviations used in this document can be found in Appendix 8.

[figure not shown]
20

PROTOCOL/AMENDMENT NO.: 004-05

#### 1.2 Schema

The study design is depicted in Figure 1.

Figure 1 MK-1654-004 Study Design

Confidential

## 1.3 Schedule of Activities

# 1.3.1 Schedule of Activities – RSV Season 1 (All Participants)

Study Period	Screening, Randomization, and Intervention						(thi	oug		llow-up 5 days po	Notes				
Visit Number/Title	1			ТС	2	Weekly TC start	3	4	5	Weekly TC end	6	ТС	7	UNSCH	See Section 8.13 for descriptions of study visits. UNSCH for respiratory infection and AESI assessment, if indicated.
	Da	y 1													a Weekly TCs will start at Day 14 and
Scheduled Day and Window (Days):			3	7 +2	14 ±2ª		90 ±5	150 ±5	180 ±2ª	240 ±5		365 +14 b		end at Day 180; each weekly TC should occur within 1 week ±2 days of the prior TC. b The Visit 7 window (+14 days) applies to participants who complete the study at this visit. For participants who continue on to RSV Season 2, see Section 1.3.2.	
Administrative Procedures															
Informed Consent	X														
Informed Consent for FBR	X														Participation in FBR is optional and consent must be obtained before collection of buccal swab DNA samples. Not applicable for participants in China (see Appendix 7).
Inclusion/Exclusion Criteria	X														
Participant Identification Card	X														Randomization number will be added to the card.
Medical History	X														
Prior/Concomitant Medication Review	X		X	X	X	X	X	X	X	X	X	X	X	X	After Day 42, only record concomitant medications associated with an SAE.
Predose NP Sample Collection for RT-PCR Testing	X (if indicated)														Collect if respiratory infection symptoms are present within 7 days before Visit 1. See Section 8.13.1.1 and Section 8.2.3.
Assignment of Randomization Number	X														

MK-1654-004-05 FINAL PROTOCOL 02-DEC-2022

PROTOCOL/AMENDMENT NO.: 004-05

Study Period	Scree Randomiz Interv				(th	roug		llow-up 5 days po	Notes						
Visit Number/Title		ТС	2	Weekly TC start	3	4	5	Weekly TC end	6	ТС	7	UNSCH	See Section 8.13 for descriptions of study visits. UNSCH for respiratory infection and AESI assessment, if indicated.		
	Da	ıy 1													a Weekly TCs will start at Day 14 and
Scheduled Day and Window (Days):	Pre dose	Dose	Post dose	3	7+2	14 ±2ª	42 +2	90 ±5	150 ±5	180 ±2ª	240 ±5		365 +14 b		end at Day 180; each weekly TC should occur within 1 week ±2 days of the prior TC.  The Visit 7 window (+14 days) applies to participants who complete the study at this visit. For participants who continue on to RSV Season 2, see Section 1.3.2.
MK-1654 or Placebo Administration		X													
Provide or Configure Device for eDiary Data Collection and Provide LAR Training			X												Review instructions for daily eDiary use with LAR (see Section 8.3.5). Instruct LAR on how to detect AESI (see Section 8.4.8 and AESI guidance document).
Review eDiary Data with LAR				X	X	X	X								
Collect eDiary Device from LAR							2	X							For participants using a study-provided device, collect after the 42-day period.
Safety Procedures															
Full Physical Examination including Weight and Length	X														
Brief Directed Physical Examination including Weight and Length					X		X	X	X		X		X	X c	Measure weight and length at all visits. c Perform brief directed examination at an unscheduled visit if necessary.
Vital Signs	X		X		X		X	X	X		X		X	X	See Section 8.3.2.
30-minute Postdose Safety Observation			X												Performed by blinded site staff only. Postdose vital signs should be repeated after the observation period.

MK-1654-004-05 FINAL PROTOCOL 02-DEC-2022

PROTOCOL/AMENDMENT NO.: 004-05

Study Period	Scree Randomiz Interv				(th	roug		llow-up 5 days po	Notes						
Visit Number/Title	1			ТС	2	Weekly TC start	3	4	5	Weekly TC end	6	ТС	7	UNSCH	See Section 8.13 for descriptions of study visits. UNSCH for respiratory infection and AESI assessment, if indicated.
Scheduled Day and Window (Days):	Pre dose Dose Post dose		3	7+2	14 ±2ª	42 +2		150 ±5	180 ±2ª	240 ±5		365 +14 b		
 
a Weekly TCs will start at Day 14 and end at Day 180; each weekly TC should occur within 1 week ±2 days of the prior TC.
 
b The Visit 7 window (+14 days) applies to participants who complete the study at this visit. For participants who continue on to RSV Season 2, see Section 1.3.2.
 
	
AE/SAE Review	2	X	•	X	X	X	X	X	X	X	X	X	X	X	
Venous Blood for ADA and Additional ADA Characterization				X (if indicated)										X	Collect if participant experiences a Grade 3 or 4 anaphylaxis/ hypersensitivity AESI on Day 2-42. See Section 8.4.8.1 and Appendix 2.
Respiratory Pathogen Asse	ssments										1	1	1		
Surveillance for Respiratory Infection Symptoms				X	X	←Weekly TC→						Determine if participant had respiratory symptoms or was seen in a clinical setting. Weekly TC after the Day 7 visit through Day 180. See Section 8.2.1.			
Respiratory Infection Assessment				X (if indicated)							X	Required if respiratory infection symptoms require further assessment. See Section 8.2.2.			
NP Sample Collection for RT-PCR Testing					X (if indica			cate	ed)					X	Collect if respiratory infection symptoms are observed. See Section 8.2.2.2 and Section 8.2.3. See Appendix 7 for Chinaspecific requirements.

PROTOCOL/AMENDMENT NO.: 004-05

Study Period	Screening, Randomization, and Intervention			Follow-up (through 365 days postdose)									Notes		
Visit Number/Title	1		TC	2	Weekly TC start	3	4	5	Weekly TC end	6	тс	7	UNSCH	See Section 8.13 for descriptions of study visits. UNSCH for respiratory infection and AESI assessment, if indicated.	
	Day 1													a Weekly TCs will start at Day 14 and	
Scheduled Day and Window (Days):	Pre dose	Dose	Post dose	3	7 +2	14 ±2ª	42 +2	90 ±5	150 ±5	180 ±2ª	240 ±5	300 ±5	365 +14 b		end at Day 180; each weekly TC should occur within 1 week ±2 days of the prior TC.  b The Visit 7 window (+14 days) applies to participants who complete the study at this visit. For participants who continue on to RSV Season 2, see Section 1.3.2.
Pharmacokinetics/Immunogenicity/Pharmacodyna															All participants will be randomly assigned by IRT to 1 of the 2 blood sampling groups (Group 1 or Group 2), then assigned to 1 of the 2 testing subgroups (a or b). Collect predose from randomized participants only.
Group 1															
Group 1a:							,								
Group 1a Venous Blood for MK-1654 PK	X				X				X						
Group 1a Venous Blood for ADA	X								X						See Section 4.2.1.4.1.
Group 1a Venous Blood for SNA	X				X				X						Not applicable for participants in China (see Appendix 7).
Group 1b:		•	U												
Group 1b Venous Blood for MK-1654 PK	X				X				X						
Group 1b Venous Blood for ADA	X								X						See Section 4.2.1.4.1.

PROTOCOL/AMENDMENT NO.: 004-05

Study Period	Screening, Randomization, and Intervention			Follow-up (through 365 days postdose)									Notes		
Visit Number/Title	1			тс	2	Weekly TC start	3	4	5	Weekly TC end	6	тс	7	UNSCH	See Section 8.13 for descriptions of study visits. UNSCH for respiratory infection and AESI assessment, if indicated.
Scheduled Day and Window (Days):	Pre dose	Dose	Post dose	3	7+2	14 ±2ª	42 +2	90 ±5	150 ±5	180 ±2ª	240 ±5		365 +14 b		a Weekly TCs will start at Day 14 and end at Day 180; each weekly TC should occur within 1 week ±2 days of the prior TC. b The Visit 7 window (+14 days) applies to participants who complete the study at this visit. For participants who continue on to RSV Season 2, see Section 1.3.2.
Group 2															
Group 2a:		1	1		I	I	1	1	l	1	I	1	1	I	T
Group 2a Venous Blood for MK-1654 PK	X								X		X				
Group 2a Venous Blood for ADA	X								X		X				See Section 4.2.1.4.1.
Group 2a Venous Blood for SNA	X								X		X				Not applicable for participants in China (see Appendix 7).
Group 2b:															
Group 2b Venous Blood for MK-1654 PK	X								X		X				
Group 2b Venous Blood for ADA	X								X		X				See Section 4.2.1.4.1.
Future Biomedical Researc	h														
Buccal Swabs (DNA) for FBR	X														Should be obtained predose on randomized and FBR-consented participants only. However, it can be collected at any later study visit after randomization. Not applicable for participants in China (see Appendix 7).

ADA=antidrug antibodies; AE=adverse event; AESI=adverse event of special interest; DNA=deoxyribonucleic acid; eDiary=electronic diary; FBR=future biomedical research; IRT=interactive response technology; LAR=legally acceptable representative; NP=nasopharyngeal; PK=pharmacokinetics; RSV=respiratory syncytial virus; RT-PCR=reverse transcriptase-polymerase chain reaction; SAE=serious adverse event; SNA=serum neutralizing antibodies against RSV; TC=telephone call; UNSCH=unscheduled visit.

MK-1654-004-05 FINAL PROTOCOL 02-DEC-2022

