# 8.3.1 Physical Examinations Including Length and Weight

A complete physical examination and brief directed physical examinations will be conducted by an investigator or medically qualified designee and consistent with local requirements. Length and weight will also be measured and recorded.

The complete physical examination should include an assessment of the head, eyes, ears, nose and throat, skin, lymph nodes, neurological system, and musculoskeletal system as well as auscultation of the heart and lungs, and an examination of the abdomen.

The brief directed physical examination should include a general assessment for respiratory distress, auscultation of the heart and lungs, and examination of the abdomen.

Investigators should pay special attention to clinical signs related to previous serious illnesses.

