PROTOCOL/AMENDMENT NO.: 004-05

Table 17 AESI: Rash Severity Grading Scale

	Severity Grade				
AESI Term	Grade 1	Grade 2	Grade 3	Grade 4	
Acute generalized exanthematous pustulosis (AGEP)	Not applicable	Not applicable	Severe or medically significant but not immediately life-threatening; hospitalization or prolongation of existing hospitalization indicated; limiting routine activities such as feeding	Life-threatening consequences; urgent intervention indicated	
Drug eruption	Lesions covering <10% BSA; topical intervention indicated	Lesions covering 10–30% BSA; oral intervention indicated	Lesions covering >30% BSA; IV intervention indicated	Not applicable	
Drug reaction with eosinophilia and systemic symptoms (DRESS)	Not applicable	Not applicable	Severe or medically significant but not immediately life-threatening; hospitalization or prolongation of existing hospitalization indicated; limiting routine activities such as feeding	Life-threatening consequences; urgent intervention indicated	
Erythema multiforme	Target lesions covering <10% BSA and not associated with skin tenderness	Target lesions covering 10-30% BSA and associated with skin tenderness	Target lesions covering >30% BSA and associated with oral or genital erosions	Target lesions covering >30% BSA; associated with fluid or electrolyte abnormalities; ICU care or burn unit indicated	
Generalized rash of exfoliative nature (including dermatitis exfoliative and exfoliative rash)	Not applicable	Erythema covering >90% BSA without associated symptoms	Erythema covering >90% BSA with associated symptoms (eg, pruritus or tenderness); limiting routine activities such as feeding	Erythema covering >90% BSA with associated fluid or electrolyte abnormalities; ICU care or burn unit indicated	
Stevens-Johnson syndrome	Not applicable	Not applicable	Skin sloughing covering <10% BSA with associated signs (eg, erythema, purpura, epidermal detachment, and mucous membrane detachment)	Skin sloughing covering 10–30% BSA with associated signs (ie, erythema, purpura, epidermal detachment, and mucous membrane detachment)	

PRODUCT: MK-1654

PROTOCOL/AMENDMENT NO.: 004-05

	Severity Grade			
AESI Term	Grade 1	Grade 2	Grade 3	Grade 4
Toxic epidermal necrolysis	Not applicable	Not applicable	Not applicable	Skin sloughing covering ≥30% BSA with associated symptoms (eg, erythema, purpura, or epidermal detachment)

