Urticaria (hives or welts)	Urticarial lesions covering <10% BSA; topical intervention indicated	Urticarial lesions covering 10-30% BSA; oral intervention indicated	Urticarial lesions covering >30% BSA; IV intervention indicated	Not applicable
AESI=adverse event(s) of special interest; BSA=body surface area; ICU=intensive care unit; IV=intravenous.				

C Confidential

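### After the 30-minute observation no scheduled examination specifies looking at the skin, so rash AESI, a primary safety endpoint, is detected mainly through prompted caregiver reports

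*Combined protocol and SAP*

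**What the plan says.** Section 1.3.1 schedules the row "Brief Directed Physical Examination including Weight and Length" at Visits 2 to 7 (Days 7, 42, 90, 150, 240 and 365). Its footnote on unscheduled visits reads "Perform brief directed examination at an unscheduled visit if necessary". That footnote settles when the examination is done. What it covers is in Section 8.3.1: "The brief directed physical examination should include a general assessment for respiratory distress, auscultation of the heart and lungs, and examination of the abdomen". The same section gives skin a place only in the other type of examination: "The complete physical examination should include an assessment of the head, eyes, ears, nose and throat, skin, lymph nodes". Section 1.3.1 schedules that one predose only.

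The synopsis and Section 3 list "Rash AESI from Days 1 through 42 postdose" as a primary safety endpoint. Table 17 in Section 10.3.5 grades most of its terms by extent of skin involved; Grade 1 urticaria, for example, is "Urticarial lesions covering <10% BSA; topical intervention indicated".

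Rash is otherwise ascertained in these ways:

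- Blinded site staff watch for an immediate rash for 30 minutes after dosing (Sections 8.1.8.1 and 8.3.4).
- The caregiver is instructed at Visit 1 and records rash AESI in the eDiary through Day 42 (Section 8.3.5).
- The site asks about rash AESI by telephone on Day 3 (Section 8.3.6).
- A rash reported in the eDiary or on a weekly call obliges the site to telephone, after which an on-site assessment may or may not follow (Section 8.4.8.2).
- Photographs are mandatory once a rash AESI is suspected or confirmed on evaluation (Section 8.4.8.2.1).

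**The concern.** At two visits within or at the end of the rash window, Day 7 and Day 42, trained staff already have the infant in front of them for an examination. As written, that examination does not include the organ that defines the endpoint. A site or home-visit provider that follows the text exactly can complete both visits without a deliberate look at the skin.

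Two other provisions add to this. Section 8.3.5 lets the investigator assess severity from what the caregiver entered or said, and on-site assessment after a report is conditional, so a grade that depends on body surface area could be assigned without staff having seen the rash. Section 8.13.5 allows a healthcare vendor to carry out visits at home following the schedule of activities, with documentation sent to the investigator. There the written content of the examination matters most.

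At stake are the completeness and uniformity across sites of the rash AESI counts. Section 4.2.1.2 explains that rash was made an AESI because earlier antibodies in this class were associated with such events.

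**Working it through.** The plan states no figure for rash detection, so there is none to reproduce. The check has two parts: a comparison of the texts, and an illustration of size.

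**Texts side by side**

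| Item | Source | Finding |
|---|---|---|
| Scheduled post-dose examinations | 1.3.1 | 6, all brief directed |
| Of these, at or inside Days 1 to 42 | 1.3.1 | 2 (Day 7 +2, Day 42 +2) |
| Of the 6, with skin in the listed content | 8.3.1 | 0 |
| Staff-performed post-dose checks that name rash | 8.3.4 | 1 (30 minutes, Day 1) |
| Rash terms graded with reference to body surface area | Table 17 | 6 of 8 (not AGEP or DRESS) |

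With 3,300 infants, 3,300 × 2 = 6,600 brief examinations are planned at these two visits. Those at Visit 3 that fall on Day 43 or 44 lie just outside the window.

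**Illustration of size**

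Inputs from the plan: 1,100 placebo and 2,200 MK-1654 infants (Section 9.9), and a 95% CI for the difference (Section 9.6.2). Assumptions, none of them from the documents: true rash AESI rates of 1.0% on placebo and 2.0% on MK-1654, with caregiver reports capturing a share s of events in both arms.

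Formula: chance that the CI excludes zero ≈ Φ[(d − 1.96·SE₀)/SE₁]. Here d is the observed difference, SE₀ uses the pooled proportion, and SE₁ uses the two separate proportions.

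- s = 100%: d = 0.0100, SE₀ = 0.004727, SE₁ = 0.004232. The argument is 0.17, giving about 57%.
- s = 70%: rates 0.7% and 1.4%, d = 0.0070, SE₀ = 0.003965, SE₁ = 0.003549. The argument is −0.22, giving about 41%.
- Range: s = 90% gives about 52%; s = 50% gives about 30%.

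**What two inspections would recover**

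Assume that onset is uniform over the 42 days, that a rash stays visible for D days with D from 2 to 7, and that inspection finds every visible rash. Two inspections then catch 2D/42 of the events that caregivers miss.

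- D = 2: 4/42 = 9.5%. Captured share 0.70 + 0.30 × 0.095 = 72.9%, chance about 43%.
- D = 7: 14/42 = 33.3%. Captured share 0.70 + 0.30 × 0.333 = 80.0%, chance about 47%.

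The recovery is thus roughly 2 to 6 percentage points of a 16-point loss. Even this is generous, because it credits staff with noticing none of these rashes under the present wording, and because missed rashes are probably the short-lived ones.

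**The case against.** The strongest reply is that the plan already has a layered system for rash: staff observation after dosing, a trained caregiver, an eDiary through Day 42, a Day 3 call that names rash, eDiary and AE review with staff, and photographs once an AESI is suspected. Section 8.4 makes the investigator and designees responsible for detecting AEs. Section 8.13.5 prefers site visits partly so that a suspected AESI is seen in person. Section 8.3.1 says what the examination should include and forbids nothing more. Further procedures may be in the AESI guidance document, which is not available here. All of this stands. It shows that detection is prompted and structured, but not that staff inspect the skin in a uniform way after Day 1.

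A reader might infer more than the documents support:

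- *That rash is found only if a caregiver reports it.* The 30-minute observation and the investigator's duty to detect AEs contradict this.
- *That unscheduled AESI visits ignore the skin.* The schedule provides such visits explicitly ("UNSCH for respiratory infection and AESI assessment, if indicated"). For a suspected rash AESI, Sections 8.4.8.2 and 8.4.8.2.1 make the skin the object of the visit and require photographs of it.
- *That the injection site is missed in the same way.* Its solicited window is Days 1 to 5 and the first scheduled visit is Day 7, so adding it to this examination would not serve that endpoint.
- *That the comparison is biased towards MK-1654.* Caregivers, investigators and assessing staff are blinded, so missed events should be similar in proportion in both arms.
- *That the Grade 3 to 4 dermatology referral would often be missed.* Those grades generally mean extensive lesions, skin sloughing or severe illness, which a caregiver is unlikely to overlook.
- *That the 12% versus 10% rash rates quoted for palivizumab in Section 2.2 indicate the likely size.* They concern rash of any kind under a monthly-dosed antibody in high-risk children, whereas Table 5 lists specific diagnoses.

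**Conclusion.** The gap is real but limited. After the 30-minute observation, no scheduled examination through Day 42 specifies skin inspection, so ascertainment of rash AESI relies mainly on prompted caregiver reports, and on-site confirmation is conditional.

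The consequence is lower observed rates in both arms and a less sensitive comparison. No formal test is affected: Section 9.6.2 names no Tier 1 events and treats Tier 2 intervals as descriptive. The fall from about 57% to 41% depends entirely on the assumed rates and on the assumed 70% reporting (about 30% to 52% for reporting of 50% to 90%). It measures the assumed loss; what the change would recover is much smaller. The case for changing the text is that staff ascertainment of a primary safety endpoint becomes uniform, including at vendor home visits, at almost no cost. It does not rest on a large gain in sensitivity.

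**What to change.** In Section 8.3.1, with a matching note in Section 1.3.1, add to the brief directed examination at Visit 2 (Day 7) and Visit 3 (Day 42): inspection of the skin, with estimated percentage of body surface area if a rash is present. Record findings that meet Table 5 as AESI when onset is within Days 1 to 42; the onset condition handles Visit 3 examinations on Days 43 and 44. No change is needed for the injection site or for unscheduled AESI visits.

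The cost is one line of text, one note, an eCRF check box and about a minute at visits where the infant is already being examined, with no extra visit or staff. The downside is slightly more nonserious rash recorded in both arms. Two inspections cover two days of a 42-day window and will miss transient lesions, so the eDiary and telephone prompts remain the main source.
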